Visit 5: GnRH): **Baroreflex and RAS testing**

Visit 6: GnRH): **Baroreflex and RAS testing**

Visit 1: Screening, informed consent, orientation:

We will describe the study in detail. Subjects will fill out a medical history form (including medications) so we can make sure it is safe for the participant to be in this study. They will have a pregnancy test at no cost and if eligible for the study and decide to participate, we will teach them how to give a self-injection of Antagon, a drug that will be used in this study. We will also orient the participant to where the research studies will be done and demonstrate the equipment and procedures that will be used for the study.

Visit 2. Transvaginal ultrasound. The subjects will undergo evaluation using transvaginal ultrasound. We will perform transvaginal ultrasound using a linear probe on a Phillips 3-D ultrasound on all subjects. There are no known risks associated with this procedure. The procedure is painless and will require approximately twenty minutes to perform. The ultrasound examination will be performed in the Yale Center for Reproductive Medicine by a gynecologist on the staff of the Yale New Haven Hospital and who is accredited by the American Institute for Ultrasound in Medicine. The ultrasound will be a focused exam looking only at the ovaries. With the subject's permission, any incidental pathology noted at the time of the exam will be sent to the subject's private gynecologist for possible further evaluation. All follicles and/or cystic structures are measured. Ovarian volume is calculated as the measure of a prolate ellipsoid. Ovarian morphology is determined by the methods described in the literature for identifying polycystic ovaries in women with PCOS (3, 4).

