Visit 3. Oral glucose tolerance test. Subjects will undergo an **OGTT at The John B. Pierce Laboratory** to quantify glucose tolerance and insulin resistance. These tests are done in the early proliferative phase of the menstrual cycle in cycling women. A standard (3 hour) OGTT will be conducted to determine glucose tolerance in all subjects within 2 weeks of the start of the study. One hour will be added for postural acclimation and insertion of the IV for a total of a 4 hour visit. Blood samples for serum concentration of glucose and insulin will be drawn at baseline prior to ingestion of a 75g glucose beverage (Glucose Drink; Azer Scientific, Morgantown, PA) and at every 30-minute time point following drinking for three hours. A total of 45ml (3 tablespoons) will be drawn.

Visits 4-6 (Visits 5 and 6 are identical to Visit 4):

Protocols 1A-B: Autonomic function: Baroreflex testing (Fig 9). We will examine **autonomic function** in our human subjects at **rest** (cardiovagal), during **Valsalva maneuver** (sympathetic), during the **modified Oxford protocol** (sympathetic, **Fig 9**) (20, 23, 33, 42) and with **integrated baroreflex** response during **LBNP** (23, 103). Our primary measure of SNSA is peripheral nerve activity, as measured by **muscle sympathetic nerve activity (MSNA)**. We will also determine HR, BP (EKG and beat-to-beat), and a catheter will be inserted into a forearm vein for blood sampling. Following the instrumentation period, resting HR, pulse (or R-R) interval (PI), BP, and MSNA will be recorded for 10 minutes, and a blood sample drawn for analysis of S_[E₂], progesterone (S_[P₄]), sex hormone binding globulin, (P_[SHBG]), albumin, free (P_[free]) and bound (P_[T]) testosterone, S_[ALD], serum angiotensin converting enzyme (S_[ACE]), angiotensinogen (S_[ANG]), renin, (P_[Renin]), PRA, P_[ANG II], norepinephrine (P_[NE]), epinephrine (P_[EPI]), electrolytes, creatinine (Cr) and osmolality (P_[Osm]). After the first blood sample and a **30-min rest phase**, subjects will begin a seven-minute period of **rest with paced breathing** (12 breaths per minute) while HR, BP and MSNA are measured (**Fig 9**).

[figure not shown]

Figure 9. Modified

The subjects will synchronize breathing to a metronome set to a cadence of ~12 breaths per minute (0.2 Hz). Following baseline measurements, subjects will perform two **Valsalva maneuvers**. Methods are described in Procedures.

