Integrated baroreflex assessment (LBNP) (Aim 1). After the modified Oxford protocol, we will assess integrated baroreflex function during incremental LBNP. Although low-level LBNP has been used to isolate cardiopulmonary baroreceptor input, arterial baroreceptors appear to be involved even at very low levels of LBNP (51, 96) so we use the term “integrated” to acknowledge the limitations of distinguishing cardiopulmonary versus arterial baroreceptor functions (23, 88, 103), and it is not the goal of these studies to distinguish the contributions of these respective baroreceptor inputs. **LBNP protocol:** During a 30-minute rest period after the SNP and PE infusions, microneurography electrode is removed, and subjects are instrumented in the left arm for the measurement of forearm blood flow (FBF, 87). We will measure baseline variables, tilt the subjects to 7° head down (HDT), return the subject to supine, then apply LBNP at -10, -20, -30 and -40 mm Hg (for 4 min each) in descending order. Heart rate, BP (beat-to-beat), PI and SkBF are measured continuously, and calf volume (circumference, to determine the extent of lower level volume shift and ensure relaxed muscles during LBNP). Blood sample is taken prior to and at the end of each stage of LBNP for the measurement of $S_{[ALD]}$, $S_{[ACE]}$, $S_{[ANG]}$, $P_{[Renin]}$, PRA, $P_{[ANG]}^{[1]}$, $P_{[NE]}$, $P_{[EP]}^{[1]}$. FBF is measured at 30-sec intervals, at rest and during the entire LBNP protocol. The total blood taken is 160 ml per visit. With FBF and BP data, we compute forearm vascular resistance (FVR) and conductance (FVC). If subjects experience presyncopal symptoms or if BP falls by 20% of baseline, we discontinue the study. If the test is stopped early we use the slopes generated from the completed levels of LBNP, but exclude data collected during symptoms or exaggerated BP falls. To determine peripheral vascular responses we analyze FVR and FVC as functions of LBNP. We will also determine changes in peripheral vascular responses by examining changes in HR as functions of SBP and LBNP (i.e. Δ HR/ Δ SBP or Δ LBNP). **LBNP** has been approved under HIC #0512000875.

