Vascular: a. claudications or history of peripheral vascular disease, b. abdominal or thoracic aortic aneurysm, or repair of same, c. cerebral aneurysm, vascular malformations, d. hypertension, systolic or diastolic.

Gastrointestinal: a. GI malignancy, b. hepatitis, current, c. splenomegaly from any cause, d. Cholecystitis, e. current diverticulosis or diverticulitis, inflammatory bowel disease, ulcerative colitis, Crohn's disease,

Infectious Disease: any ongoing intercurrent infection.

Hematologic/Oncologic: a. receiving chemotherapy or radiation therapy, b. any metastatic malignancy, c. anemia (hematocrit < 35), d. thrombocytopenia or thrombocytosis, e. neutropenia, f. hematologic malignancy, g. bleeding dyscrasias.

Neurologic: a. history of cerebral vascular accident with any neurologic sequels, b. uncontrolled seizures (e.g., more than 1 seizure/year), c. transient ischemic attacks, d. dementia, e. neurologic conditions producing dyscoordination, peripheral neuropathy, or myopathy.

Endocrine: a. diabetes mellitus, b. any untreated endocrinopathy.

Renal: a. chronic renal diseases, b. any history of renal disease or impairment, c. current urinary tract infection.

Musculoskeletal: a. inflammatory arthritis history (e.g., rheumatoid, psoriatic, Reiters), b. any history of pathologic fractures, including vertebral compression fractures.

Pharmacologic: a. any illegal drug use (self report), b. alcohol use greater than an average of 4 oz/day over 30 days.

8. How will **eligibility** be determined, and by whom?

Eligibility will be determined by the P.I. ([name]) and by the Co-I ([name]) by interview with potential subjects. We will conduct an initial interview by phone and the subject will fill out a medical history questionnaire during the orientation session. In this interview we will ask the subject if she has been diagnosed with PCOS or insulin resistance, we will ask her approximate height and weight. We will ask her name and if she has any other health issues that would preclude her from participating in the study.

9. **Risks:** Describe the reasonably foreseeable risks, including risks to subject privacy, discomforts, or inconveniences associated with subjects participating in the research.

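### The anemia exclusion is a hematocrit value, but eligibility is decided by interview and no listed visit measures hematocrit, so as written it can catch only anemia already diagnosed

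*Combined protocol and SAP*

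**What the plan says.** The hematologic exclusions in Section V.7 include "anemia (hematocrit < 35), d. thrombocytopenia or thrombocytosis, e. neutropenia". Anemia is the only one of these four conditions with a number attached: "anemia (hematocrit < 35".

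Section V.8 says the principal investigator and a co-investigator determine eligibility "by interview with potential subjects". It then describes the instruments: "We will conduct an initial interview by phone and the subject will fill out a medical history questionnaire during the orientation session".

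The screening visits in Section V.3 are these:
- Visit 1 has a history form and one test: "They will have a pregnancy test at no cost and if eligible for the study and decide to participate".
- Visit 2 is a transvaginal ultrasound.
- Visit 3 is the oral glucose tolerance test (OGTT): "Blood samples for serum concentration of glucose and insulin will be drawn at baseline prior to ingestion of a 75g glucose beverage". On volume it says "A total of 45ml (3 tablespoons) will be drawn".

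Visits 4 to 6 are the three test visits. For these the LBNP section says "The total blood taken is 160 ml per visit". The Blood sampling paragraph under Procedures gives a different figure, approximately 60 ml, without saying whether that is per visit.

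**The concern.** A hematocrit threshold needs a blood measurement. A woman with unrecognized anemia has nothing to report on a phone screen or a history form. The same exclusion list marks illegal drug use as ascertained by self-report, so the authors labelled self-report in at least one place where they meant it. The anemia item carries no such label.

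What is at stake is participant safety. A woman who passes screening goes on to up to three visits, each with repeated blood draws and LBNP down to -40 mm Hg. The study rates its own risk as moderate rather than minimal. The risk section names only infection and bruising for blood sampling, and it gives no cumulative blood volume per woman.

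**Working it through.** **Step 1. Is there any step that yields a hematocrit?** The relevant sections, side by side:

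- Phone screen (VII.4): height, weight, diagnosis of PCOS or insulin resistance, regularity of periods, smoking, medications.
- History form (VIII.a): race/ethnicity, history, allergies, medications, hospitalization, exercise, alcohol, smoking, periods. No laboratory results are listed.
- Records search (VII.2): run by a separate team that passes no protected information to the researchers, so it supplies no chart value.
- Visits 1 to 3 (V.3): history and pregnancy test; ultrasound; glucose and insulin.
- Visits 4 to 6 (V.3, baroreflex, LBNP and RAS paragraphs): sex steroids, SHBG, albumin, renin-angiotensin-aldosterone measures, catecholamines, electrolytes, creatinine, osmolality.
- Assay methods (Procedures, Plasma hormones): ELISA, spectrophotometry and HPLC assays, no blood count.

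Hematocrit occurs once in the document, in the exclusion itself. Platelet and neutrophil counts are likewise in no panel.

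**Step 2. How much blood is drawn?** The plan states volumes per visit and no per-woman total, so there is no stated total to reproduce.

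Inputs: OGTT volume 45 ml (Visit 3); three test visits (Visits 4 to 6; each woman is tested three times); volume per test visit either 160 ml (LBNP section) or about 60 ml (Blood sampling paragraph, if per visit).

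Formula: total = OGTT volume + number of test visits × volume per test visit.

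- With 160 ml: 45 + 3 × 160 = 45 + 480 = **525 ml**.
- With 60 ml: 45 + 3 × 60 = 45 + 180 = **225 ml**.
- Aim 5 only, one test visit at 160 ml: 45 + 160 = 205 ml.

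The two three-visit totals differ by 525 − 225 = 300 ml, entirely because of the conflict between the two paragraphs. The screening testosterone sample and the Aim 4 draws have no stated volume and are in neither total.

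**Step 3. To whom do the three-visit totals apply?** To women completing three LBNP visits: the 2 × 36 = 72 planned in Aims 1 and 2, and Aim 3 women if the same sampling is used there.

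**Step 4. Over what period?** AE-PCOS women may start at their convenience and are tested on Days 1, 3 and 10, so the 3 × 160 = 480 ml can fall within 10 days. Controls have their baseline early in a cycle and start suppression on cycle days 26-28, so their draws are more spread out.

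**The case against.** The strongest reply is that V.7 introduces its list as histories or conditions. On that reading the hematocrit figure only defines which known anemia excludes, and the criterion works on history. Part of this stands: a reader might infer that the rule cannot be applied at all, and that goes too far, because known anemia is still caught. But then the text should say that the criterion is history-based.

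A second reply is that absence from the visit lists is weak evidence. Visits 1 to 3 also omit the serum testosterone and blood pressure that other criteria need, and V.8 is plainly incomplete, since ultrasound, OGTT and the pregnancy test also decide eligibility. This also stands in part. The supportable claim is that no listed step measures hematocrit, not that none is ever done. The history form itself, the authentication section that the criteria point to, the figures and the removed pages could not be checked. Still, the one method V.8 states cannot apply the threshold V.7 states.

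A third reply is that the harm is unquantified. That is fair. A reader might infer that 525 ml is the established exposure, that all 72 women are harmed, or that undetected anemia biases the sympathetic and renin-angiotensin results. The documents support none of these. The volume is contradicted elsewhere in the protocol. The 72 women are unscreened by measurement, which is different from anemic. No anemia rate or effect size is given. The LBNP section already stops for presyncope or a 20% fall in blood pressure, and comparisons of a woman with herself would largely share a stable anemia.

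**Conclusion.** The point holds in a limited form. As written, the anemia exclusion can detect only anemia that has already been diagnosed, and the same is true of the thrombocytopenia, thrombocytosis and neutropenia exclusions. This is more than a missing detail, because the stated way of deciding eligibility does not produce the value that the stated criterion requires.

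The blood volume for a woman completing three LBNP visits is 525 ml or 225 ml, depending on which paragraph governs. The second total assumes that the 60 ml is per visit. The screening gap does not depend on which figure is right.

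The number of women with undetected anemia is unknown. Any effect on presyncope stops, or on the Control versus AE-PCOS contrast, remains inference. The point changes no sample size or analysis.

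**What to change.** Reconcile V.7, V.8 and the visit schedule. Keep the protocol's own hematocrit criterion, decide it on a value measured before Visit 4, and say so in V.8. One way is a small anticoagulated or capillary sample at Visit 3, where venous access is already in place. The OGTT samples themselves are for serum and cannot give a hematocrit.

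State in the same amendment how the other laboratory-type exclusions (platelets, neutrophils) are ascertained. If a history-only criterion is what the investigators intend, V.7 should say that instead.

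Reconcile the 160 ml and 60 ml figures and give one cumulative volume per woman for each aim.

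Cost: one minor added assay, a short amendment, and a few more screen failures.

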Statistical analyses: Univariate statistics [mean (SD)] will be generated on all study variables first, which will determine the normality or the heteroscedacity of the data. Data will be analyzed using SPSS 21 statistical software, that includes calculations to compensate for missing data, and Prism (GraphPad) curve fitting software where appropriate. **Data analysis.** The slopes of the linear regressions for PI-SBP (cardiovagal baroreflex gain), PI-LBNP (integrated baroreflex gain), resting MSNA, slopes for MSNA-DBP (sympathetic baroreflex gain during Oxford and Valsalva), will be compared between treatment conditions (GnRH antagonist vs. GnRH antagonist+T and between groups (Control vs AE-PCOS) using a 2-way repeated measures ANOVA with supplemental *post hoc* testing with Tukey's HSD test. **Sample size.** The desired statistical test is two-sided, and we assume an alpha level of =0.01 to account for multiple comparisons (37). In our laboratory, we observed effect sizes (SD) of PI-SBP intercept (with n=4) of 0.39 (0.16), our most stringent variable. A sample size of 15 women per group will allow us $\geq 80\%$ statistical power ($1-\beta > 0.9$) to test within group comparisons, and this same sample size will allow $[1-\beta]=0.80$ to distinguish any between-group differences from chance alone (29). Due to the technical challenges of performing microneurography on multiple occasions in obese women, we overestimate and account for a $\sim 20\%$ failure rate, so we will recruit 18 subjects per group. **R&R:** **1) GnRH antagonist suppression/hormone add-back** is the gold standard and most reliable method to control sex hormones in young women. **2) Microneurography** is the gold standard and most sensitive and reliable available measure for MSNA. **3) Lower body negative pressure** and the **Modified Oxford Technique** are the gold standards and most sensitive and reliable available measures of autonomic function in humans. We will report our methods and findings in detail and **full transparency** to permit others to reproduce and extend our findings. **Sex as a biological variable:** Only women are included in these studies because AE-PCOS is a female-specific disorder.

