Aim 1: Statistical analyses: Univariate statistics [mean (SD)] will be generated on all study variables first, which will determine the normality or the heteroscedacity of the data. Data will be analyzed using SPSS 21 statistical software that includes calculations to compensate for missing data, and Prism (GraphPad) curve fitting software where appropriate. **Data analysis.** The slopes of the linear regressions for PI-SBP (cardiovagal baroreflex gain), PI-LBNP (integrated baroreflex gain), resting MSNA, slopes for MSNA-DBP (sympathetic baroreflex gain during Oxford and Valsalva), will be compared between treatment conditions (GnRH antagonist vs. GnRH antagonist+T and between groups (Control vs AE-PCOS) using a 2-way repeated measures ANOVA with supplemental *post hoc* testing with Tukey's HSD test. **Sample size.** The desired statistical test is two-sided, and we assume an alpha level of =0.01 to account for multiple comparisons (37). In our laboratory, we observed effect sizes (SD) of PI-SBP intercept (with n=4) of 0.39 (0.16), our most stringent variable. A sample size of 15 women per group will allow us \geq 80% statistical power ($1-\beta > 0.9$) to test within group comparisons, and this same sample size will allow $[1-\beta]=0.80$ to distinguish any between-group differences from chance alone (29). Due to the technical challenges of performing microneurography on multiple occasions in obese women, we overestimate and account for a $\sim 20\%$ failure rate, so we will recruit 18 subjects per group. **R&R:** **1) GnRH antagonist suppression/hormone add-back** is the gold standard and most reliable method to control sex hormones in young women. **2) Microneurography** is the gold standard and most sensitive and reliable available measure for MSNA. **3) Lower body negative pressure** and the **Modified Oxford Technique** are the gold standards and most sensitive and reliable

available measures of autonomic function in humans. We will report our methods and findings in detail and **full transparency** to permit others to reproduce and extend our findings. **Sex as a biological variable:** Only women are included in these studies because AE-PCOS is a female-specific disorder.

Aim 2: Statistical analyses: We use ANOVA as described in Protocols 1. **Sample Size** is based on calculations in Aim 1, as the Aim 1 variables are the more stringent.

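### Missing sessions are left to the software, but the named repeated-measures ANOVA would discard usable nerve recordings from any woman with one failed session

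*Combined protocol and SAP*

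**What the plan says.** Missing data are covered by one clause, given twice. Section V.12 (Statistical Considerations, Aim 1) says the analysis will use "statistical software that includes calculations to compensate for missing data". The Statistical analyses paragraph in Section V.3 repeats it: SPSS 21 is software "that includes calculations to compensate for missing data". No imputation method, missingness assumption, analysis set or sensitivity analysis is given.

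The same paragraphs name the analysis: a two-way repeated-measures ANOVA with Tukey's test, comparing treatment conditions (antagonist versus antagonist plus testosterone) and groups (Control versus AE-PCOS). Aims 2 and 3 refer back to it. Section V.3 (Experimental Protocols) has each woman tested three times, on Days 1, 3 and 10, in four cells of 18.

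On numbers, the plan states "A sample size of 15 women per group will allow us" the stated power at two-sided alpha 0.01. It then explains the recruitment figure: "Due to the technical challenges of performing microneurography on multiple occasions in obese women", it allows about 20% failure and recruits 18 per group. The only specific rule for incomplete data covers lower body negative pressure stopped early within a session, not a session with no recording.

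**The concern.** Naming a package's capability is not naming a method. A standard repeated-measures ANOVA needs a value at every level of the repeated factor, so a woman with two good nerve recordings and one failed one contributes nothing unless her missing value is filled in beforehand. The plan expects such failures, since the nerve must be found again at each of three visits within a 60-minute limit.

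At stake are the resting MSNA and MSNA-DBP slope outcomes, which are central to Aim 1; Section V.3 calls MSNA its primary measure of sympathetic activity. Women who had undergone invasive recording would lose their usable data, and the count of complete women could fall below the 15 on which the stated power rests. By how much depends on what the 20% means, and the documents do not say.

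**Working it through.** **Inputs from the documents.** 15 evaluable and 18 recruited per cell; about 20% failure; alpha 0.01 two-sided; stated power above 0.90 within group (the same sentence also says at least 80%) and 0.80 between groups; three sessions, two of whose conditions are named in the ANOVA text.

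**The plan's own figure.** 15 × 1.20 = 18 reproduces the recruitment number. Dividing instead, 15 / 0.80 = 18.75, gives 19. The inflation acts on women, which points towards a per-woman reading without stating it.

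**Expected complete women per cell.** This is 18 × p, where p is the chance that a woman has all analysed sessions. The chance of at least 15 is the upper tail of Binomial(18, p). Per-session rows assume that failures are independent across sessions.

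| Reading of failure | p | Expected complete | P(at least 15) | Recruits for an expected 15 |
|---|---|---|---|---|
| 20% per woman | 0.80 | 14.4 | 0.50 | 19 |
| 10% per session, two sessions | 0.9² = 0.81 | 14.6 | 0.54 | 19 |
| 20% per session, two sessions | 0.8² = 0.64 | 11.5 | 0.07 | 24 |
| 5% per session, three sessions | 0.95³ = 0.857 | 15.4 | 0.75 | 18 |
| 10% per session, three sessions | 0.9³ = 0.729 | 13.1 | 0.24 | 21 |
| 20% per session, three sessions | 0.8³ = 0.512 | 9.2 | 0.005 | 30 |

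On the per-woman reading, the chance that all four cells reach 15 is 0.50⁴ ≈ 0.06. The break-even for an expected 15 is 1 − 15/18 = 16.7% per woman, or 1 − (15/18)^(1/3) = 5.9% per session over three sessions.

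**Power.** The documents give no effect size for MSNA, so I took the standardised effects that the stated power at n = 15 implies (noncentral t, alpha 0.01): about 1.13 for a paired contrast at 0.90, and 1.33 for a between-group contrast at 0.80.

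| Complete women per cell | Within group | Between groups |
|---|---|---|
| 15 | 0.90 | 0.80 |
| 14 | 0.87 | 0.76 |
| 12 | 0.77 | 0.67 |
| 9 | 0.55 | 0.48 |

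These figures are back-solved, not derived from the plan's data. The one effect stated, "effect sizes (SD) of PI-SBP intercept (with n=4) of 0.39 (0.16), our most stringent variable", taken as a difference over its SD is 0.39/0.16 = 2.44. That gives power of about 0.98 (between) and 0.999 (within) even at n = 9. It concerns PI-SBP, not MSNA, and does not reproduce the stated 0.80 between groups.

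**What a likelihood analysis would save.** For a contrast c of session means with covariance R, the complete-case variance is proportional to c′Rc / (1 − q)³, where q is the per-session failure rate. The likelihood variance is proportional to c′V c, where V is the inverse of the information averaged over all patterns of observed sessions. I assumed correlations of 0.5 (Day 1 with Days 3 and 10) and 0.7 (Day 3 with Day 10), with known covariance. The complete-case variance is then about 1.4 to 1.5 times larger at q = 20%, and about 1.1 times at q = 7.2%, the per-session rate equivalent to 20% per woman (1 − 0.8^(1/3)). A simulation at 20% per session, n = 18 and the same correlations gave 1.31 to 1.44.

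**Which outcomes are exposed.** The PI-SBP slope comes from ECG and beat-to-beat pressure (Procedures, Cardiovascular variables). Lower body negative pressure is run after the electrode has been removed (Section V.3, Integrated baroreflex assessment). So PI-SBP, PI-LBNP and the renin-angiotensin hormones do not depend on the nerve recording, provided the rest of the visit goes ahead. They lose data only through missed visits or withdrawals.

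**The case against.** The strongest reply is that the plan has already allowed for this. It inflates the number of women, describes 20% as an overestimate, and on that reading falls short by 15 − 14.4 = 0.6 of a woman. At 14 complete women the back-solved within-group power is still 0.87. A woman whose nerve is hard to record is also likely to fail repeatedly, and such correlation raises the complete count above 9.2. All of this stands, and it limits the size of the point.

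A reader might infer that the trial will keep only about nine women per cell and have 55% power. The documents do not support that. It needs 20% per session, independence, all three sessions in the model (the ANOVA text names two conditions) and an effect back-solved from the stated power. Nor does nerve-recording failure undermine the whole analysis: the variable that sizes the study is PI-SBP, which does not use the electrode.

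It might also be said that the plan does not exclude imputing before the ANOVA. That is true, but it does not specify it either, and a capability of the package leaves the choice open until the data are seen.

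Finally, a mixed model might be expected to remove bias. If failure depends on body size, it does not do so by itself. Failure that differs only by group does not by itself bias within-woman changes in each group.

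**Conclusion.** The point holds for the MSNA and MSNA-DBP outcomes. The plan pairs an expected failure rate of about 20% with an analysis that drops incomplete women and names no method for them. On the reading that the arithmetic favours, 20% per woman, the shortfall against 15 is small: 14.4 expected, an even chance of at least 15 in a cell, and back-solved power down by about 0.03 within and 0.04 between groups if 14 remain. On the per-session reading the expected count is 11.5 or 9.2, which marks the unfavourable end of an assumed range that the documents neither state nor exclude. What does not depend on the reading is that usable recordings from partly complete women are discarded when a standard method would keep them. The precision regained depends on the assumed failure rate and correlations.

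**What to change.** Replace the missing-data sentence and the ANOVA, in both Section V.3 and Section V.12, with a linear mixed model using all available sessions (SPSS MIXED): REML, unstructured covariance over Day 1, Day 3 and Day 10, and small-sample degrees of freedom. State that it assumes missingness can be explained by the observed data. Add baseline body size as a covariate if recording failure is thought to depend on it. Say which sessions enter each contrast, and report how many women and sessions contribute.

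Define the 20% as per woman or per session, then restate the expected evaluable number and power separately for the MSNA outcomes and for those that do not need the electrode.

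The cost is SAP wording, slightly more analysis work in the same software, and probably a slightly less favourable stated evaluable number. Any increase in recruitment follows only if the restated power is judged too low. The model keeps partial records but does not recover failed recordings.
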